Screening Meeting. Potential participants who have met the initial criteria of the study (based on the telephone interview) will be invited to the study center at a mutually convenient time. During this time, the participant and a member of the research team will meet in a private, quiet conference room or office. The individual will be provided the informed consent form, and its contents will be described to the potential participant. The participant will then have the opportunity to review it, and if they choose to participate in the study, they will be asked to provide written consent. Although the participant will be asked to sign the informed consent, the participant will be told that they will not be asked to participate if their body measurements, blood pressure, or plasma chemistries (see Enrollment Criteria) do not meet the study criteria. If the participant has provided consent, we will then measure the participant's height, weight, waist circumference, and blood pressure. Next, if the participant is fasted for at least 10 hours, we will ask if a trained individual can draw a small blood sample (15 mL; 1.5 tubes) so that we may measure blood chemistries (glucose, HDL, triglyceride). All samples will be coded to maintain participant anonymity. If the participant's anthropometrics, blood pressure, or plasma chemistries do not meet the study criteria, they will be told that do not meet the study criteria.

Potential participants who meet the criteria, will be contacted within a few days after their screening meeting to provide them with their blood and body measurement results and inform them of their eligibility to participate in the study. Consistent with our CLIA exemption, blood results will be

provided in a categorical manner (i.e. "normal", "marginally high", "high") rather than providing actual blood concentrations of lab values (see Subjects Results Sheet). Potential participants having any blood values outside of the "normal range" will be directed/encouraged to follow-up with their own physician. Those having body measurements, blood pressure, and blood values within acceptable limits (see Inclusion/Exclusion criteria), will be invited to participate in the study. Subjects will be included or excluded based on a best-fit of the inclusion and exclusion criteria (an example of best-fit would be if a potential male subject's waist circumference is 101 cm, which is outside the specified waist circumference inclusion range for MetS participants they might still be included in the study if they meet all other inclusion and exclusion criteria more closely than other potential subjects). Participants will be read one phone script if they qualify and another phone script if they do not qualify (see Participant Eligibility Phone Script attachment). Potential participants who qualify for the study will be communicated a message as follows: I have your screening results. "Congratulations, you meet the eligibility criteria for our clinical trial. Your body measurements, blood pressure, and fasting blood chemistries of glucose, triglyceride, and cholesterol were all within the specified range. Your glucose falls in the [category], triglyceride fall in the [category], and cholesterol falls in the [category]. A summary of your results has been prepared for you, which you will receive when you come in for your next visit. We look forward to and are thankful for your participation." Potential participants who do not qualify will be provided the following message: "I have your screening results. Unfortunately, you do not meet the eligibility criteria for our clinical trial. Your body measurements, blood pressure, glucose, triglyceride, and/or cholesterol were not within the eligible range. Your glucose falls in the [category], triglyceride fall in the [category], and cholesterol falls in the [category]. A summary of your results has been prepared for you. Please let me know if you would like to drop by the study center to collect a hard copy of your information or if you would like them e-mailed to you. Thank you so much for your time and effort." All individuals regardless of study eligibility will be encouraged to consider sharing these results with their physician.

In the event that a participant is telephoned and is unavailable, a message will be left requesting a callback at a convenient time or that at a member of the study team will try calling again at a later time. No confidential or sensitive information will be shared with third parties or left on answering machines.

Intervention Timeline. Each participant will complete a 2-phase (GTE vs placebo) randomized, crossover study. Each study intervention will consist of 3 study visits (Day 0, 14, 28) over a 4-wk period. After completing the first intervention, participants will undergo a wash-out period (1 month), and afterwards, begin the alternative intervention.

On Day 0, participants will come to the study center in a fasted state and provide a blood sample (45 mL) to measure endotoxin, TMAO, LBP, sCD14, a panel of clinical chemistries, and catechins. Following the blood collection, participants will be instructed on how to complete a 3-d diet record as well as be informed about maintaining a low-polyphenol diet throughout the duration of the intervention. Participants will then be provided a 2-wk supply of confections, for which they will be instructed to consume 6 confections each day (2 confections/meal; 1 g GTE/d).

On Day 14, participants will return to the study center in the fasted state and return any uneaten confections. Another blood sample (45 mL) will be collected for measurement of biomarkers as described above. Participants will then be asked to complete another 3-d diet record and be reminded to keep maintaining a low-polyphenol diet.

Prior to the final visit on Day 28, participants will collect a stool sample during the preceding 3 days. Participants will collect their stool samples in the comfort of their home and will be asked to return the samples on ice or meet with study personnel to return the samples to the study center within 24 h upon

collection. On Day 28, participants will come to the study center in the fasted state. A fasting blood sample (60 mL) will be collected to measure the biomarkers mentioned above along with analysis of white blood cell inflammatory genes. Following blood collection, participants will perform a gut permeability test. Participants will consume a test beverage that contains sucrose (40 g), lactulose (5 g), mannitol (1 g), sucralose (1 g), and erythritol (1 g) dissolved in water (250 mL). After ingestion of the beverage, participants will be instructed to collect their urine from 0-5 and 6-24 hours in the provided containers.

After completing the first intervention, participants will partake in a wash-out period (1 month) and then repeat the same study procedures (i.e. Day 0, Day 14, Day 28), but will receive the alternative confection (i.e. GTE vs placebo). During each study visit, participants will have access to drinking water and use of the restroom as needed. Details about each study visit and associated test trials that will occur is explained below:

Intervention Phase / Test Confections. During the 4-wk intervention, participants will receive a GTE-rich or placebo (no GTE containing) confection. Confections will be low-carbohydrate and low-calorie. Each serving (6 g) provides <8 kcal, while delivering 1 g of decaffeinated GTE. The catechin profile (82% catechins (w/w); 63% EGCG, 18% EGC, 10% ECG, 9% EC) is similar to that of freshly brewed green teas. Sucrose will be the main carbohydrate source because sugar alcohols alter microbiota composition⁸¹ and would confound interpretation. Decaffeinated GTE was chosen to minimize potential side effects such as excess caffeine consumption or caffeine/drug interactions that could result from comorbidity management of metabolic conditions. Placebo confections will be identical to GTE-rich confections, but without GTE. Confections will be packaged in single-serve, oxygen impermeable containers, and coded for study blinding. Participants will be asked to store the confections in the refrigerator to maintain quality and freshness.

Participants will be asked to consume 6 confections each day (2 with each meal) for 4 weeks. Consumption of 6 GTE-rich confections is equivalent to delivering 1 g GTE/d. At the first visit, participants will provide a fasting blood sample and then receive a 2-wk supply of confections. Halfway through the intervention (d 14), participants will visit the study center in a fasted state (10-12 h). Participants will return any leftover confections. After a 5 min stabilization period, a single fasting blood sample will be collected following procedures stated above. After collecting blood, the participants will be provided the final 2-wk supply of confections. At the conclusion of the intervention phase (d 28), participants will perform a gut permeability test and provide another fasting blood sample. Compliance will be evaluated based on the number of confections returned throughout the study as well as objectively by measuring catechin/catechin-metabolites in the plasma. To ensure randomization, a random number generator will be used to randomly assign the sequence by which the participant will complete each of the interventions.

Gut Permeability Test. On the morning of testing at d 28 of the intervention, participants will arrive at the study center after abstaining from food and only consuming water for 10-12 hours. A gut permeability test will be conducted as described⁸⁵. Upon arrival, participants will be asked to empty their urinary bladder. Subsequently, they will then be asked to ingest a drink containing 40 g sucrose, 5 g lactulose, 1 g mannitol, 1 g sucralose, and 1 g erythritol dissolved in water (250 mL). Within 2-hours after ingesting the sugar test beverage, participants will be asked to consume an additional 500 mL of water. Participants will be instructed to abstain from foods that contain artificial sweeteners during the 24-hour period. Urine will be collected from 0-5 and 6-24 hours in sterile containers with 10% thymol (inhibit bacterial growth). For each urinary collection period, participants will be provided 2-L urine collection bottles and a cooler with ice packs to store collected urine until they return their samples the next day.

Sampling Handling. For the entire study (~3 months), including the screening phase and completion of both interventions (GTE vs placebo), we plan to collect a total of 315 mL or 1.3 cups of blood. At screening, 15 mL of blood will be obtained to ensure adequate sample to perform biochemical measures of eligibility. During each 4-wk intervention, we will collect a total of 150 mL or 0.6 cups. At day 0 and 14 we will collect 45 mL (0.2 cups) and at day 28 we will collect 60 mL (0.25 cups). All blood will be collected into evacuated blood collection tubes. The greater volume of blood collected at day 28 is necessary to ensure that there is adequate blood to perform the same analyses as for day 0 and 14 as well as for additional analyses (e.g. white blood cell inflammatory markers). During blood collection, participants may feel an initial pain when inserting the needle, bruising around the insertion area, lightheadedness, or fainting, which are common when donating blood.

Urine will be collected in provided containers (VWR) containing 10% thymol to inhibit bacterial growth. Feces will be collected using a commercial commode specimen collection system (Fisher Scientific). Briefly, the collection kit consists of the necessary materials (e.g. disposable spatula, gloves, waste bag) for participants to easily and hygienically collect their stool without contaminating the sample or themselves. We will provide participants with coolers with ice to store their stool samples for up to 24 h after collection. We will then have the participants return their stool samples to the study center or coordinate with study personnel to meet at a public and mutual location to return their samples within 24 h after collection. Volumes of urine will be recorded and fecal mass and observations will be recorded based on the Bristol Stool Chart. ¹⁰³

During each blood collection, plasma and white blood cells will be obtained by centrifugation, and then transferred to cryogenic storage tubes. Serum samples will be obtained by allowing the blood to clot, followed by centrifugation and transfer to cryogenic storage tubes. Tubes will be stored at -80°C until analysis can be completed. Analyses will include triglyceride, HDL, liver function (aminotransferases), renal function (creatinine, BUN), CBC, glucose, insulin, pro-inflammatory gene expression, catechins (EGCG, ECG, EGC, EC), catechin-metabolites (e.g. valerolactones, catechinderivatives), serum endotoxin, TMAO, LBP, and sCD14. Urine will be stored at -80°C until analysis can be completed. Analysis from urine will include sucrose, mannitol, lactulose, sucralose, and erythritol. Fecal samples will be stored at -80°C until analysis can be completed. Feces analysis will include microbiota composition, myeloperoxidase, calprotectin, and SCFAs. Remaining plasma, serum, urine, and fecal samples not used for these analyses will be archived for 5 years at -80 C in the event we decide to measure additional inflammatory, antioxidant, or microbiota related markers. Appropriate notation has been made in the informed consent to alert participants that we will be archiving specimens and that they have the right to refuse our use of these specimens for future analyses. Lastly, approval from OSU IRB will be sought via a protocol amendment prior to the analysis of any additional biomarkers not specified herein.

Privacy/Confidentiality. For all data and records that are a part of this study, a number (i.e. code) will be assigned to each participant, which will only be available to research personnel. Any records containing the names of participants will be stored in a locked filing cabinet or on a password-protected computer in the PI's laboratory or office. Research personnel under the supervision of the PI and the PI himself will be the only individuals that have access to this information. The names of participants will not be used for publication in any form. The records will be maintained until the data are published, up to a maximum of five years. All archived samples will be coded, but the key linking the code to each participant's identifiable information will have been destroyed. In addition, participants will be instructed that their participation in this study is voluntary and that they may withdraw at any time without prejudice. Data (food records and biochemical values) obtained from this study will be stored on a computer in the PI's laboratory. In addition, a backup of digital data will be stored on the PI's

computer in his office. Both computers are password-protected and both doors are locked when work areas are not in use.

E. Internal Validity

For all data and records that are a part of this study, a number (i.e. code) will be assigned to each participant. Test confections will be assigned a code as well. This will minimize measurement bias when performing analysis of dietary records and biochemical markers, because all samples/records will be coded. The codes will only be broken once data analysis has been completed and verified by the PI.

IV. Literature Cited

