We will conduct a *randomized double-blind, placebo-controlled crossover trial* in metabolic syndrome (MetS) and healthy individuals. We will enroll adults with (n = 20) and age- and gender-matched healthy (n = 20) men and women (18-65 y). Participants will be block-randomized to receive GTE-rich (1 g GTE) or placebo confections and will be asked to consume the confections daily for 4 wk, while instructed to abstain from all tea varieties and follow a low-polyphenol diet. Blood will be collected at day 0, 14, and 28 for metabolic assessments and safety monitoring by assessing a serum chemistry panel [e.g. liver function (aminotransferases), renal function (creatinine, BUN), CBC, glucose, insulin, insulin resistance 19. At the same time points, blood pressure and anthropometrics will be assessed, and dietary nutrient and flavonoid intakes will be evaluated from 3-d food records using NDSR dietary analysis software and the NCC Flavonoid and Proanthocyanidin database as we described. On day 28, participants will provide a 3-d fecal sample. Following blood collection, they will complete a gut permeability test and collect urine through day 29 (described below). Upon completing these procedures, participants will undergo ~1-mo wash-out before repeating the study identically, but with crossover to the alternate treatment.

GTE-rich Confections. The [name] and [name] labs have previously developed a starch-based GTE-rich confection⁷³ as a successful catechin delivery system. For this application, we will modify this

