Enrollment Criteria. Male and female adults with MetS (18-65 y) having no history of liver, cardiovascular disease, or cancer will be enrolled. They are expected to meet >3 established criteria for MetS,82 and we will enroll those fulfilling these specific inclusion criteria to improve participant homogeneity: fasting glucose (100-126 mg/dL), waist circumference (>89 cm or 102 cm for F/M), HDL-C (<50 or <40 mg/dL in F/M), triglyceride >150 mg/dL. Although elevated blood pressure is a symptom/criteria for MetS, only those individuals having blood pressure <140/90 mmHg will be enrolled to avoid those having with Stage 2 hypertension.⁸³ Age- and gender-matched healthy adults (19-25 kg/m²) will also be enrolled. They will be normoglycemic (glucose <100 mg/dL), normotensive (<120/80 mmHg) and normolipidemic (HDL-C >50 mg/dL or >40 mg/dL in F/M; triglyceride <150 mg/dL). Major exclusion criteria for all participants include: concurrent tea consumption (Camellia sinensis or herbal varieties); vegetarian; user of dietary supplements, prebiotics, or probiotics within past month; hemochromatosis; any gastrointestinal disorders or surgeries; chronic diarrhea; Parkinson's disease; smoker; alcohol consumption (>2 drinks/d); recent use of antibiotics or antiinflammatory agents. We will also not enroll any participants using any medications to manage diabetes, hypertension, or hyperlipidemia (e.g. statins, metformin, ACE inhibitors), any medications known to be contraindicated for use with green tea ingestion (e.g. antipsychotic medications [Clozapine, lithium, Diazepam], blood thinning medications [Warfarin], high blood pressure medications [nadolol], and monoamine oxidase inhibitors [selegiline]), women who are pregnant or lactating, or have initiated or changed birth control in the past 3 months.

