Recruitment. We will recruit participants through posted flyers, e-mail, electronic and newsprint advertisements (e.g. campus student and faculty/staff newspapers, local and regional newspapers), word of mouth, and social media (e.g. Facebook). The posted advertisements will instruct interested participants to complete an online eligibility survey or call the study center ([name] Laboratory, Department of Human Sciences) to obtain further information. During the phone-in hours, a trained individual (i.e. project coordinator or graduate assistant) will be available to describe the study and determine preliminary qualification by conducting a scripted phone interview (e.g. do you take dietary supplements?, do you smoke?; see *Phone Script* attachment). The individual will record answers and assess whether or not the person calling is likely or not to be an acceptable study participant. If the caller and the interviewer agree that the caller should participate, the prospective participant will be invited to a screening meeting, where the study will be fully described and the individual will be provided a consent form to complete prior to any involvement in the study procedures. Data collected during this phase will include participant's age, health status, physical activity, and contact information (see *Informed Consent* attachment).

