Power Calculation and Data Analysis. We performed a power analysis using serum endotoxin (day 28) as the primary outcome. Mean serum endotoxin of MetS and healthy adults was used to predict a conservative 30% improvement by GTE in MetS persons; this corresponds to a 10 EU/mL decrease in endotoxin in MetS. Simulations were used to estimate power based on 20 healthy and 20 MetS adults randomized to treatment vs control in a 50/50 ratio, respectively. Based on a linear model with treatment and health status, and within-subject measures, we will have >90% power (α =0.05) to detect the primary contrast of interest (GTE vs placebo in MetS adults) and additionally, >85% power (α =0.05) to detect an interaction between treatment and health status. Most data will be analyzed by linear mixed effects models (LMMs) with random effect for subjects (to account for repeated measures) and fixed effects for health status, gender, GTE treatment, time period, and their interactions. Multivariate regression analysis will define correlations between study variables with consideration of potential covariates. Statistical significance for all analyses will be set at P≤0.05.

C. Measurement/Instrumentation

Anthropometric Parameters and Blood Pressure. At screening, participants will rest for 15 minutes prior to determining blood pressure using an automated cuff. BMI will be calculated from height determined from a wall-mounted stadiometer and weight from a calibrated scale. Waist circumference will be assessed at the level of the umbilicus using a nonflexible measuring tape.

Blood Chemistries. At screening, fasting plasma glucose, triglyceride, and HDL-cholesterol will be measured by spectrophotometry utilizing validated clinical assays (Pointe Scientific). At day 0, 14, and 28 of the interventions, collected blood will be sent to The Ohio State University Medical Center for metabolic evaluations by assessing a serum chemistry panel [e.g. [e.g. liver function (aminotransferases), renal function (creatinine, BUN), CBC, glucose, insulin, insulin resistance⁷⁹].

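### Age is a matching variable but is missing from the mixed model, so between-person health-status main effects keep age variance and are exposed to any leftover age gap

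*Combined protocol and SAP*

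**What the plan says.** Section III.A (Research Design) describes the comparators as "age- and gender-matched healthy (n = 20) men and women", over an age range of 18 to 65 years. Section III.B (Enrollment Criteria) repeats the matching: "Age- and gender-matched healthy adults (19-25 kg/m²) will also be enrolled". Neither place says whether matching is by pair or by frequency, or how close the ages must be.

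Section III.B (Power Calculation and Data Analysis) sets out the model: "Most data will be analyzed by linear mixed effects models (LMMs) with random effect for subjects", with "fixed effects for health status, gender, GTE treatment, time period, and their interactions". Gender is there; age and a matched-pair term are not. Covariates are mentioned only in the next sentence: "Multivariate regression analysis will define correlations between study variables with consideration of potential covariates". That sentence names no variable and describes a separate analysis.

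Age is available. Section III.B (Recruitment) states: "Data collected during this phase will include participant's age, health status, physical activity, and contact information".

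The primary contrast is GTE versus placebo in MetS adults on day-28 serum endotoxin. The only powered test that involves health status is its interaction with treatment. Section III.C (Microbiota Composition and Function) also plans to report an effect of MetS status itself, on total bacterial abundance by qPCR.

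**The concern.** MetS versus healthy is not a randomised comparison. Age matching is the design's protection against age confounding, and its benefit reaches the reported standard error only if the analysis takes account of age. Leaving age out has two possible consequences for a between-person main effect.

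- **Precision.** Age variance stays in the between-person error. With well-matched groups the estimate is unbiased, but its standard error is overstated and the test is conservative.
- **Bias.** With no stated tolerance, the groups may differ in mean age, and the health-status estimate then absorbs the difference. The protocol itself gives a reason to expect pressure in that direction: its section on significance puts MetS at about 35% of Americans but 50% of those over 60.

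At stake is the reading of health-status main effects, for example on bacterial abundance or on endotoxin level. The trial's primary result is not at stake.

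**Working it through.** **1. The plan's own power figures.** The plan states more than 90% power for the primary contrast and more than 85% for the interaction. These cannot be reproduced, because no SD, within-subject correlation or healthy-group effect is given. Solving backwards with a difference of 10 EU/mL and two-sided alpha 0.05 (sidedness assumed):

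- Primary contrast, paired t, n = 20: the SD of within-person differences can be at most 13.1 EU/mL.
- Interaction, two-sample t on within-person differences, 20 versus 20, healthy effect assumed to be 0: at most 10.3 EU/mL.

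The two claims are compatible: at SD 10, power is 98.9% and 86.9%. Neither calculation involves between-person variance, so an age term does not alter them.

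**2. Assumed inputs for the main effect.** Between-person SD 10 and within-person SD 7. The latter gives an SD of differences of 7 × √2 = 9.9, which is compatible with the stated power. The between-person SD has no support in the documents.

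**3. Precision.** Averaging each person over two periods, the variance per person is 10² + 7²/2 = 100 + 24.5 = 124.5. The unadjusted SE for 20 versus 20 is √(124.5 × 2/20) = 3.53. If age explains a share R² of the between-person variance, the SE is multiplied by √[(100(1 − R²) + 24.5)/124.5]:

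| R² (assumed) | Calculation | SE factor | Narrowing |
|---|---|---|---|
| 0.10 | √(114.5/124.5) | 0.959 | about 4% |
| 0.20 | √(104.5/124.5) | 0.916 | about 8% |
| 0.30 | √(94.5/124.5) | 0.871 | about 13% |

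The ceiling, with no within-person error at all, is √(1 − R²), or 5%, 11% and 16%.

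**4. Bias from a leftover age gap.** With ages assumed uniform over 18 to 65, the SD of age is 47/√12 = 13.6 years. The bias in between-person SD units is r × gap/13.6. For a 5-year gap:

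| r (assumed) | 0.1 | 0.2 | 0.3 | 0.4 | 0.5 |
|---|---|---|---|---|---|
| Bias (SD) | 0.04 | 0.07 | 0.11 | 0.15 | 0.18 |

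**5. Simulation check.** A balanced crossover with the same SDs, ages matched within 3 years, a true main effect of 8.0 and 2,000 runs per setting:

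- Matched ages: no bias. The mean model SE is 3.49 without age and 3.37 with it at r = 0.3, and 3.50 and 3.12 at r = 0.5. At r = 0.5 the true sampling SD is 3.17 either way, so the unadjusted SE is the one that is wrong.
- MetS group about 5 years older: the unadjusted estimate is 8.95 at r = 0.3 and 9.67 at r = 0.5, which is 12% and 21% too large. With age it is 7.90 and 7.94.
- Interaction (true value −10): the estimate stays near −10 throughout. Letting age predict the within-person difference changes its SE from 3.11 to 3.10 with matched ages, and from 3.10 to 3.15 with the gap.

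**The case against.** The strongest reply is that age is handled by design, that this is legitimate if less efficient, and that nothing primary or powered changes. Most of that stands. With close matching the unadjusted analysis is unbiased and merely conservative. The bias argument needs a leftover gap that the documents do not report, and every figure above depends on an age-outcome association that they do not give.

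Several stronger readings are tempting but not supported:

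- *That every MetS-versus-healthy comparison is affected.* The treatment by health-status interaction is built from within-person differences, so an additive age effect cancels. Age would matter there only if it modified the GTE effect or, slightly, if periods were incomplete.
- *That MetS-status effects across all outcome domains are affected.* Section III.C promises an interaction for catechin metabolism and GTE effects for inflammation. For endotoxin, Anticipated Results predicts a larger decrease in MetS, again an interaction. Community structure is analysed by multivariate methods that a mixed-model term would not reach.
- *That the best-fit entry rule in the screening section loosens age matching.* That rule concerns inclusion and exclusion criteria, and its example is waist circumference. It does not mention matching.
- *That the gain is the full √(1 − R²).* That ignores within-person error, which age cannot remove.

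The sentence on potential covariates does not answer the point, since it names none and concerns correlations.

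**Conclusion.** The point holds in a narrow form. One of two matching variables is absent from the model, and the matching tolerance is unstated. Health-status main effects estimated by the mixed model therefore have overstated standard errors and no protection from a residual age gap. Under the assumed SDs, adjustment narrows their intervals by about 4% to 13% for R² of 10% to 30%. A 5-year gap would bias them by 0.04 to 0.18 SD for correlations of 0.1 to 0.5. If age is unrelated to the outcome, nothing is gained. Of the two consequences, bias is the better reason to act, because the comparison is not randomised. The primary contrast, the interaction and the stated power are essentially unaffected, so this is a minor improvement.

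**What to change.** Add continuous age as a fixed effect next to gender in every mixed model that reports a health-status main effect. Enter it additively and say so, because the current wording crosses the listed terms with one another and age need not join those interactions. State the matching method and age tolerance in Section III.B. Specify both before the treatment codes are broken, so that the choice of covariate is not made after seeing results.

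The cost is one between-person degree of freedom in 40 people, with no new data and no change to sample size or procedures. If age turns out to be unrelated to the outcome while a 5-year gap remains, the SE of the main effect rises slightly (3.50 to 3.56 in the simulation).
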